# 9. STUDY EVALUATIONS

## 9.1. Study Procedures

### 9.1.1. Overview

Patients participation will include:

1. The pretreatment (screening) phase will be 30 days for all laboratory tests and radiographic imaging phase and up to 60 days for orchectomy and bone marrow evaluation.
2. The open label treatment phase will extend from the first day of the first course of R-CHOP to a maximum of 6 courses.
3. The consolidation phase will extend from the first day of the first course of Intermediate-dose MTX to the end of radiotherapy.
4. The follow-up phase will begin after the completion of the consolidation phase. Follow-up will continue until disease progression (PD), patient withdrawal, death or the study completion (expected to be 36 months from the date of the last patient's end of therapy).

Hematology results must be available and reviewed by the investigator to evaluate for possible hematological toxicity.

All subjects will be monitored for adverse events throughout the study and for 30 days after the end of treatment.

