### Adverse Events

Adverse events will be reported by the subject (or, when appropriate, by a caregiver, surrogate, or the subject's legally acceptable representative) for the duration of the study.

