### **Physical Examination**

Any clinically significant abnormalities persisting at the end of the study will be followed by the investigator until resolution or until reaching a clinically stable endpoint.

**Safety and feasibility of treatment:** severe hematological toxicities (grade 3-4) expected.

Grading of toxicity will be defined according to the International Common Toxicity Criteria, version 3.0 (12/12/2003)

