#### **Serious Adverse Event (SAE)**

A serious adverse event as defined by ICH is any untoward medical occurrence that at any dose meets any of the following conditions:

- Results in death
- Is life-threatening (The subject was at risk of death at the time of the event. It does not refer to an event that hypothetically might have caused death if it were more severe.)
- Requires hospitalization or prolongation of existing hospitalization
- Results in persistent or significant disability / incapacity
- Is a congenital anomaly / birth defect

Medical and scientific judgment should be exercised in deciding whether expedited reporting is also appropriate in situations other than those listed above. For example, important medical events may not be immediately life threatening or result in death or hospitalization, but may jeopardize the subject or may require intervention to prevent one of the outcomes listed in the definition above. Any adverse event is considered a serious adverse event if it is associated with clinical signs or symptoms judged by the investigator to have a significant clinical impact.

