## 11.2. Procedures

### 11.2.1. All Adverse Events

All adverse events other than disease progression will be reported from the time a signed and dated informed consent form is obtained until 30 days after the 1st dose of study drug. All events that meet the definition of a serious adverse event will be reported as serious adverse events, regardless of whether they are protocol-specific assessments.

All adverse events, regardless of seriousness, severity, or presumed relationship to study therapy, must be recorded using medical terminology in the source document and the CRF. Whenever possible, diagnoses should be given when signs and symptoms are due to a common etiology (e.g. cough, runny nose, sneezing, sore throat, and head congestion should be reported as "upper respiratory infection"). Investigators must record in the CRF their opinion concerning the relationship of the adverse event to study therapy. All measures required for adverse event management must be recorded in the source document and reported according to sponsor instructions.

All grade 3 and 4 adverse events, considered related, must be followed until resolution of the event, or the event improves to a grade 2 or better. The events of interest in the table above of grade 2 or higher will be followed until grade 1 or better. The unresolved aforementioned events will be followed for a maximum of 6 months.

Sections of the CRFs containing adverse event information will be submitted by the investigator to a representative of the sponsor. Serious adverse event reports will be submitted as described in Section 11.2.2, Serious Adverse Events.

The investigator-Sponsor must report adverse events to the appropriate Independent Ethics Committee/Institutional Review Board (IEC/IRB) that approved the protocol unless otherwise required and documented by the IEC/IRB. The Investigator-Sponsor assumes responsibility for appropriate reporting of adverse events to regulatory authorities. The Investigator-Sponsor shall also report all serious adverse events to the pharmaceutical companies providing the study medication.

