## 11.2.2. Serious Adverse Events and SUSAR

### Reporting of SAE

All serious adverse events occurring during clinical studies must be reported **by fax** to the sponsor IELSG (IELSG Coordinating Center, CH-6500 Bellinzona – Switzerland; Phone: +[contact] – Fax: +[contact]; E-mail: [[contact]](mailto:[contact])) by investigational staff **within 24 hours** of their knowledge of the event, using the **SAE Report Forms**, which must be signed by a member of the investigational staff.

The SAE outcome must be reported within 14 days, using the **SAE Follow up Form**. In case the SAE is still ongoing after 14 days, additional SAE Follow up Forms must be sent again to report the final outcome.

The cause of **death** of a subject in a clinical study, whether or not the event is expected or associated with the investigational agent, is considered a serious adverse event. Any event requiring **hospitalization** (or prolongation of hospitalization) that occurs during the course of a subject's participation in the clinical study must be reported as a serious adverse event, except hospitalizations for:

- a standard procedure for protocol therapy administration
- social reasons in absence of an adverse event
- surgery or procedure planned before entry into the study (must be documented in the CRF)
- study drug administration
- study related procedures defined in the protocol

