### Reporting of SUSAR

All relevant information about suspected unexpected serious adverse reactions (SUSAR's) are recorded and reported in an expedited fashion.

Events that fall into this category must be reported **within 24 hours** of occurrence **using the SAE Report Form** (see above).

It is the legal requirement of the sponsor to report SUSARs to the Competent Authorities and Ethics Committees (fatal or life-threatening within 7 days, nonfatal and non life-threatening within 15 days)

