## **12.5. Drug accountability**

After patient's registration, the study drug will directly be supplied to the clinical investigator by Mundipharma (see 5. Registration)

The clinical investigator is responsible for ensuring that all study drug (i.e., Depocyt®) received at the site is inventoried and accounted for throughout the study. Study drug must be handled strictly in accordance with the protocol and the container label and will be stored in a limited access area and under locked conditions.

Study drug should be dispensed under the supervision of investigator, a qualified member of the investigational staff, or by a hospital/clinic pharmacist. Study drug will be supplied only to subjects participating in the study. Returned study drug must not be dispensed again, even to the same subject. Study drug may not be relabeled or reassigned for use by other subjects. The investigator agrees neither to dispense the study drug form, nor store it at any site other than study sites agreed upon the sponsor.

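### Section 11.2.1 ends adverse-event reporting 30 days after the first dose, contradicting 9.1.1 and 9.4, so non-serious toxicity from most of the treatment could go unreported

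*Combined protocol and SAP*

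**What the plan says.** Three sections set a period for adverse events.

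- Section 11.2.1, the operative reporting procedure, runs from signed consent "until 30 days after the 1st dose of study drug" and covers every adverse event except disease progression.
- Section 9.1.1: "All subjects will be monitored for adverse events throughout the study and for 30 days after the end of treatment".
- Section 9.4, under Adverse Events, has events reported by the subject, a caregiver or the "legally acceptable representative) for the duration of the study".

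Serious events have a separate rule in 11.2.2: "All serious adverse events occurring during clinical studies must be reported", with no 30-day limit. SUSARs "are recorded and reported in an expedited fashion", also without one.

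Study drug is not defined in 11.2.1. Section 12.5 refers to "all study drug (i.e., Depocyt®) received at the site", and section 6.1.1 gives Depocyt only with cycles 2 to 5.

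The primary objective (2.1) is the safety and feasibility of the whole programme: R-CHOP, intrathecal liposomal cytarabine, methotrexate and radiotherapy. The safety and feasibility line in 9.4 reads "severe hematological toxicities (grade 3-4) expected".

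**The concern.** The section that tells sites what to report has the shortest window, and that window closes early in treatment. The gap is confined to non-serious events, but these are not trivial here. Section 11.1.1 makes an event serious if it meets one of the listed outcomes (death, threat to life, hospitalization, disability, birth defect) or is "associated with clinical signs or symptoms judged by the investigator to have a significant clinical impact". A grade 3-4 cytopenia found on a blood count, without signs, symptoms or admission, need not qualify. It would then fall outside 11.2.2, although 9.4 names that kind of toxicity under safety and feasibility.

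A site that follows 11.2.1 literally could stop reporting such events after the cut-off, while a site that follows 9.1.1 would continue. Toxicity rates pooled over sites would then mix different observation periods and could be too low. Events that were never recorded may be hard to recover afterwards.

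**Working it through.** **Inputs**

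- R-CHOP: six courses every 21 days (6.1.1; Attachment 9).
- Intrathecal Depocyt: with cycles 2, 3, 4 and 5 (6.1.1).
- Methotrexate: starts three weeks after R-CHOP, two courses 14 days apart (6.1.1).
- Cytotoxic CSF levels after an intrathecal dose: at least 14 days (1.2).
- Radiotherapy: 10 to 20 fractions (section 7).

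**Reproducing the plan's calendar**

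- R-CHOP day = 21 × (course − 1): 0, 21, 42, 63, 84, 105.
- Intrathecal: days 21, 42, 63, 84.
- Methotrexate: 105 + 21 = 126 and 126 + 14 = 140.

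These agree with Attachment 9.

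**Close of the 11.2.1 window**

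- Study drug read as any protocol drug, first dose on day 0: 0 + 30 = day 30.
- Study drug read as Depocyt, first dose about day 21: 21 + 30 = day 51.

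**Administrations given on or before the close** (each R-CHOP course counted as one)

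| | Close on day 30 | Close on day 51 |
|---|---|---|
| R-CHOP | 2 of 6 | 3 of 6 |
| Intrathecal | 1 of 4 | 2 of 4 |
| Methotrexate | 0 of 2 | 0 of 2 |
| Total | 3 of 12 | 5 of 12 |
| Radiotherapy after chemotherapy | none | none |

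**Intrathecal doses observed for 14 days**

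- Close on day 30: the day-21 dose has 30 − 21 = 9 days, so 0 of 4.
- Close on day 51: the day-21 dose has 51 − 21 = 30 days and the day-42 dose has 51 − 42 = 9 days, so 1 of 4.

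**Share of calendar time**

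The comparison period is day 0 to 30 days after the end of treatment, the end-point in 9.1.1. The documents do not give one start day for radiotherapy:

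- section 3.2, two weeks after methotrexate: 140 + 14 = 154;
- section 7, three weeks after chemotherapy: 140 + 21 = 161;
- Attachment 9, where the radiotherapy mark appears to fall: 165;
- synopsis, from week 24: 24 × 7 = 168.

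Day 150, the first Attachment 9 column after methotrexate, is taken as the lower limit. At an assumed five fractions a week, 10 to 20 fractions take 14 to 28 days.

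- Earliest end: 150 + 14 + 30 = day 194.
- Latest end: 168 + 28 + 30 = day 226.
- Close on day 30: 30/226 = 13.3% to 30/194 = 15.5%.
- Close on day 51: 51/226 = 22.6% to 51/194 = 26.3%.

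Starting no earlier than day 154 moves the earliest end to 154 + 14 + 30 = 198, and the upper figures to 30/198 = 15.2% and 51/198 = 25.8%.

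**Would reading 1st as last settle it?**

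Not if study drug means Depocyt. The last Depocyt dose is on day 84, and 84 + 30 = day 114, before the first methotrexate course on day 126. The anchor needs defining as well as the word.

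**The case against.** The best reply is that 1st is a slip for last and that the rest of the protocol makes a 30-day stop implausible. Section 11.2.1 itself requires every adverse event to be recorded in the source document and CRF, and the adverse-event pages to go to the sponsor, with no cut-off in either sentence. It also has related grade 3-4 events followed until they improve, for at most 6 months. Section 6.2 grades toxicity from the previous cycle for dose modification, section 9.1 requires blood counts and chemistry before each course, and section 10.2 acts on prolonged grade 3 or higher toxicity. The three windows also describe somewhat different acts: 9.1.1 speaks of monitoring, 11.2.1 of reporting.

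Much of this is fair. These provisions make it likely that some of the toxicity would be recorded somewhere, and the slip is plausible. But the documents do not say it is a slip, and none of the provisions states a different reporting period that would override the explicit one. Following up a reported event does not cause a new one to be reported, and pre-course laboratory values are not graded, attributed adverse-event reports. The distinction between monitoring and reporting does not remove the conflict, because 9.4 also speaks of reporting.

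A second objection is that 9.1.1 is itself unclear: throughout the study might include the 36-month follow-up, so an end-point 30 days after treatment would take only half of its sentence. On that reading the 30-day clause would be redundant for nearly every patient, so the end of treatment is the more natural anchor. The longer wording in 9.4 does still have to be reconciled explicitly.

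It is also true that no between-site comparison is planned. What matters is therefore possible under-counting in the pooled rates.

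**Conclusion.** The contradiction is real and must be fixed. Read literally, the only explicit reporting cut-off leaves 9 of 12 drug administrations (12 − 3) outside the window, or 7 of 12 (12 − 5) if the count starts at the first Depocyt dose. Under either reading both methotrexate courses and all radiotherapy given after chemotherapy fall outside. The window covers about 13-15% or 23-26% of the time from day 0 to 30 days after the end of treatment.

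The counts rest on the Attachment 9 calendar without delays. The percentages also rest on the radiotherapy assumptions above. Patients with bilateral disease may be irradiated during R-CHOP, so part of their radiotherapy could fall inside the window. These are shares of doses and time, not of toxicity, and the proportion of events lost cannot be computed. Site practice is unknown, since the CRF completion guidelines mentioned in 14.1 are not in the documents. The conclusion is therefore that non-serious events could be omitted, not that they would be. Reporting of serious events and SUSARs is intact.

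**What to change.** In 11.2.1, end the reporting period 30 days after the end of study treatment, defined as the last drug dose or the last radiotherapy fraction, whichever is later. This uses the end-point already in 9.1.1 and removes the dependence on what study drug means. In 9.4, add one line saying how its study-long reporting relates to that window, for example whether any non-serious events are still collected during follow-up. Put the same window in the CRF completion guidelines. Leave 11.2.2 unchanged.

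The cost is one amended sentence, one clarifying line and updated CRF guidance. Sites would enter adverse events for the full treatment period, which 9.1.1 already expects of them. No dose, schedule or treatment rule changes.

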## 11.2.2. Serious Adverse Events and SUSAR

### Reporting of SAE

All serious adverse events occurring during clinical studies must be reported **by fax** to the sponsor IELSG (IELSG Coordinating Center, CH-6500 Bellinzona – Switzerland; Phone: +[contact] – Fax: +[contact]; E-mail: [[contact]](mailto:[contact])) by investigational staff **within 24 hours** of their knowledge of the event, using the **SAE Report Forms**, which must be signed by a member of the investigational staff.

The SAE outcome must be reported within 14 days, using the **SAE Follow up Form**. In case the SAE is still ongoing after 14 days, additional SAE Follow up Forms must be sent again to report the final outcome.

The cause of **death** of a subject in a clinical study, whether or not the event is expected or associated with the investigational agent, is considered a serious adverse event. Any event requiring **hospitalization** (or prolongation of hospitalization) that occurs during the course of a subject's participation in the clinical study must be reported as a serious adverse event, except hospitalizations for:

- a standard procedure for protocol therapy administration
- social reasons in absence of an adverse event
- surgery or procedure planned before entry into the study (must be documented in the CRF)
- study drug administration
- study related procedures defined in the protocol

### Reporting of SUSAR

All relevant information about suspected unexpected serious adverse reactions (SUSAR's) are recorded and reported in an expedited fashion.

Events that fall into this category must be reported **within 24 hours** of occurrence **using the SAE Report Form** (see above).

It is the legal requirement of the sponsor to report SUSARs to the Competent Authorities and Ethics Committees (fatal or life-threatening within 7 days, nonfatal and non life-threatening within 15 days)

## 12. STUDY DRUG INFORMATION

### 12.1. Physical description of study drug(s)

DepoCyt® (Cytarabine Liposomal Injection) is a sterile sustained –release formulation of cytarabine that is manufactured by encapsulating an aqueous solution of cytarabine (ARA-C) in spherical multivesicular lipid-based particles (DepoFoam drug delivery system).

DepoCyt® injection contains cytarabine (also called cytosine arabinoside, ara-C, 4-amino-1-1-β-D-arabinofuranosyl-2(1H)-pyrimidine (C9H13N3O5, molecular weight 243.22.), which is an analogue of the nucleosides cytidine and deoxycytidine, but contains arabinose in place of the usual ribose or deoxyribose. Cytarabine is an odourless white powder that is freely soluble in water and slightly soluble in alcohol.

Cytarabine enters cells by a facilitated diffusion mechanism. Once inside the cell, cytarabine must be metabolised to a nucleotide, ara-CTP, before it can exert its effects.

Ara-CTP inhibits DNA polymerase and terminates DNA chain elongation. The cytotoxic effects are therefore specific to the S-phase of the cell cycle. This means that the cytotoxic effects are a function of concentration and duration of exposure, and prolonged exposure of cells to the drug is vital to achieve maximum activity.

The half-life of free cytarabine in the CSF is only 3.4 hours, so cytotoxic levels are maintained for less than 24 hours. Because the drug is cleared rapidly relative to flow rates within the CSF, it often does not spread well throughout the neuraxis. In contrast, DepoCyt® injection distributes well throughout the neuraxis and increases the half-life of cytarabine in the CSF over 40-fold, as shown in the pharmacokinetic study by Chamberlain et al. The concentration of cytarabine after administration of DepoCyt® injection is maintained for at least 14 days.

DepoCyt® is formulated as a sterile non- pyrogenic white to off- white suspension of cytarabine in sodium chloride 0, 9% w/v in Water for Injection. DepoCyt® is preservative free. Inactive ingredient at the respective approximate concentrations are cholesterol, 4.1 mg/mL; triolein, 1.2 mg/mL; 1,2-dioleoyl-sn-glycero-3-phosphocholine (DOPC), 5.7 mg/mL; and 1,2-dipalmitoyl-sn-glycero-3-phospho-rac-(1-glycerol) (DPPG), 1.0 mg/mL. The pH of the product falls within the range from 5.5 to 8.5.

The lipid-encapsulated aqueous chambers form spherical particles of approximately 20 µm in diameter. The particles are suspended in 5 mL of sterile NaCl, 0.9% at a concentration of 10mg/mL and stored ready to use without further dilution. DepoCyt® has the consistency and appearance of skim milk. When stored in sterile normal saline at 2° - 8° C the particles are stable for 12 months. When the particles are injected into the CSF they spread throughout the neuraxis and slowly release the cytarabine. The particles gradually degrade and disappear from the CSF, and the lipids enter the normal lipid metabolic pathways for triglycerides, phospholipids and cholesterol in the body. As a single injection of 50 mg, DepoCyt® maintains cytotoxic concentration of cytarabine in the CSF for ≥14 days in most patients, thus, IT administration of DepoCyt® is required just once every two weeks

### 12.2. Packaging

DepoCyt® suspension is provided in a 5 mL ready-to-use single-use glass vials containing 50 mg (10mg/mL) of cytarabine.

### 12.3. Labeling

The study drug label contains information to meet the applicable regulatory requirements. The label text in English/Italian is provided in Attachment 11.

## **12.4. Preparation and handling**

### **12.4.1. DepoCyte**

For additional information refer to the package insert for liposomal cytarabine (DepoCyte®). See also Attachment 3.

### **12.4.2. Rituximab**

For additional information refer to the package insert for rituximab. See also Attachment 4.

## **12.5. Drug accountability**

After patient's registration, the study drug will directly be supplied to the clinical investigator by Mundipharma (see 5. Registration)

The clinical investigator is responsible for ensuring that all study drug (i.e., Depocyt®) received at the site is inventoried and accounted for throughout the study. Study drug must be handled strictly in accordance with the protocol and the container label and will be stored in a limited access area and under locked conditions.

Study drug should be dispensed under the supervision of investigator, a qualified member of the investigational staff, or by a hospital/clinic pharmacist. Study drug will be supplied only to subjects participating in the study. Returned study drug must not be dispensed again, even to the same subject. Study drug may not be relabeled or reassigned for use by other subjects. The investigator agrees neither to dispense the study drug form, nor store it at any site other than study sites agreed upon the sponsor.

## **13. ETHICAL ASPECTS**

### **13.1. Regulatory Ethics Compliance**

#### **13.1.1. Investigator responsibilities**

The investigator is responsible for ensuring that the clinical study is performed in accordance with the protocol, current ICH guidelines on Good Clinical Practice (GCP), and applicable regulatory requirements. GCP is an international ethical and scientific quality standard for designing, conducting, recording, and reporting studies that involve the participation of human subjects. Compliance with this standard provides public assurance that the rights, safety, and well being of study subjects are protected, consistent with the principles that originated in the Declaration of Helsinki, and that the clinical study data are credible.

